11.1 Sample size

The sample-size is estimated according to previous trials with an expected between-group difference of 18 percentage points in favorable outcome (90-day mRS 0-2, 67.3% in the NS group and 49.3% in the control group).[4] Based on 0.8 power to detect a significant difference (2-sided $P=0.05$) and to compensate for nonadherence or dropout rate of 5%, we intend to enroll 120 patients per group (calculated by PASS, version 15.0, <https://passapp.io/>).

11.2 Statistical analysis

The modified intention-to-treat analysis of efficacy outcomes and safety outcomes are performed on the full analysis set, which is composed of all patients who receive randomization independent of treatment and at least 1 efficacy evaluation after enrollment. The primary outcome is also performed with sensitivity analyses, including per-protocol analysis; imputation of missing primary outcome data under the scenarios of worst possible outcome, and best possible outcome. The χ^2 test is used in the unadjusted analysis. Modified Poisson regression model with robust error estimation is used in analysis of the primary outcome and other dichotomous end points, with adjustment for prespecified covariates

(age, sex, post-IVT NIHSS scores and onset-to-needle time). The relative risk (RR) with their 95% confidence interval (95%CI) is calculated in both unadjusted and adjusted analysis. Generalized linear models (GLMs) are conducted for analyse continuous end points, including NIHSS scores, Barthel scale, blood pressure, infarction volumes, ejection fraction at each follow-up time point. The full range score on mRS is analyzed by an ordinal logistic-regression model, and odds ratio (OR) with 95%CI are calculated. Cox regression model are used for analyzing the follow-up cerebrovascular events, presented with cumulative probability of events in Kaplan Meier cures. No interim analyses are performed in this study. The missing values of baseline variables in the covariate-adjusted analyses are replaced by mean values (continous variates) or mode (dichotomous variates) only if the number of them account for less than 10% in total.

A 2-sided P value <0.05 is considered statistical significance. Because multiple comparisons potentially cause type I error, findings for secondary outcome analyses should be interpreted as exploratory. SPSS software (version 26, IBM) and R software (version 4.1.0) are used for the statistical analyses.

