3.2.2 Exclusion criteria

- (1) Massive infarction, characterized by infarction area larger than 1/3 of the effected middle cerebral artery territory and/or the cerebellum territory presented in admitted computed tomography (CT) or magnetic resonance imaging (MRI);
- (2) Intention to undergo endovascular treatment;
- (3) History of heart failure or pre-IVT brain natriuretic peptide (BNP) $\geq 500\text{pg/ml}$ or having presentations or signs indicating heart failure;
- (4) Haemorrhage during IVT, including ICH, severe digestive haemorrhage and severe respiratory haemorrhage.

- (5) Allergy to thrombolysis drugs;
- (6) Intolerant to thrombolysis due to any reasons and had to terminate thrombolysis;
- (7) Arterial puncture at a non-compressible site within previous 7 days, major surgery within previous 14 days, sever trauma, gastrointestinal or urinary tract bleeding within previous 21 days;
- (8) Cerebral infarction or myocardial infarction within previous 3 months, previous ICH including parenchymal haemorrhage, intraventricular haemorrhage, subarachnoid haemorrhage, subdural/external haematoma, etc;
- (9) Severe brain trauma, intracranial or intraspinal surgery within previous 3 months or known malignant intracranial neoplasm, giant intracranial aneurysm or arteriovenous malformation;
- (10) Persistent systolic blood pressure ≥ 180 mmHg or diastolic blood pressure ≥ 100 mmHg;
- (11) Admitted blood glucose < 2.8 mmol/L or > 22.2 mmol/L;
- (12) Defect in coagulation, for example, current use of oral warfarin with an international normalised ratio > 1.7 , or prothrombin time > 15 s, or heparins during the last 48 hours, or use of direct thrombin inhibitors or direct factor Xa inhibitors during the last 48 hours or with an elevated activated partial thromboplastin time;
- (13) Known defect of platelet or clotting function, platelet count $< 100 \times 10^9$ /L;
- (14) Stroke mimics, such as seizure and hysteria;
- (15) Brain haemorrhage identified by CT or MRI;
- (16) Any terminal illness such that patients would not be expected to survive > 1 year;
- (17) Pregnant women or nursing mother;
- (18) Poor compliance, or inability to adhere to the trial protocol or follow-up
- (19) Participating in other clinical trials within previous 3 months.

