7.2 Safety outcomes

(1) The ejection fraction evaluated by ultrasonic cardiogram within 72 hours.

[figure not shown]
(2) Death rate within 90 days.

(3) Intracranial hemorrhage and symptomatic intracranial hemorrhage within 7 days.

(4) Blood pressure fluctuation within 24 hours.

(5) Infarction edema volume evaluated by cranial CT at 24 hours.

8. Study flow diagram

AIS: acute ischemic stroke; IVT: intravenous thrombolysis; NS: normal saline.

9. Study periods

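### Section 11.2 and the synopsis give rare binary safety outcomes an adjusted robust Poisson model with no rule for an arm without events; with the usual sandwich variance that model almost always returns P<0.05 there

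*Combined protocol and SAP*

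**What the plan says.** Section 11.2 says that the modified intention-to-treat "analysis of efficacy outcomes and safety outcomes are performed on the full analysis set". For binary outcomes it then states: "Modified Poisson regression model with robust error estimation is used in analysis of the primary outcome and other dichotomous end points". The adjustment is for age, sex, NIHSS after thrombolysis and onset-to-needle time. A χ² "test is used in the unadjusted analysis", and a relative risk (RR) with 95% CI is required both with and without adjustment. The synopsis repeats the model.

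Section 7.2 lists death within 90 days and "Intracranial hemorrhage and symptomatic intracranial hemorrhage within 7 days". These are binary, and no other model is named for them. Only one kind of event gets a further method: "Cox regression model are used for analyzing the follow-up cerebrovascular events".

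Neither section 11.2 nor the synopsis has an exact test, a penalised fit, a minimum event count or a rule for an empty arm. The type of robust variance is not named. On software, section 11.2 says: "SPSS software (version 26, IBM) and R software (version 4.1.0) are used for the statistical analyses".

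**The concern.** In a robust Poisson fit, an arm with no events drives the log RR towards infinity. A sound standard error should grow with it. The sandwich standard error does not, so the Wald statistic becomes very large and P falls to almost zero, even with a single event in the trial.

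Section 2.1 makes safety part of the hypothesis. Followed as written, the plan could report one symptomatic ICH against none as a significant adjusted harm or, if the saline arm is the empty one, as a significant adjusted benefit. The χ² P value for the same table would be 0.32. With no rule in place, the choice between the two would be made after the data are seen.

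**Working it through.** **Inputs.** From section 11.1: 120 per arm, 67.3% v 49.3%, power 0.8, two-sided 0.05, 5% dropout. From section 11.2: the model, the four covariates, the χ² test and the 0.05 threshold. Event rates and covariate distributions are not in the documents and are assumed below.

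**1. The plan's sample size.** With unpooled variance, n = (1.960 + 0.842)² × (0.673×0.327 + 0.493×0.507) / 0.18² = 113.9, so 114. Then 114/0.95 = 120 per arm, as stated.

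**2. Why the standard error stays small.** Take k events among n in one arm and none in the other, without covariates. The arm with events adds 1/k − 1/n to the sandwich variance of the log RR. In the empty arm every fitted value is some m close to 0 and every residual is −m, so it adds n·m²/(n·m)² = 1/n. The total is at most 1/k, however far the estimate has diverged. The model-based variance instead contains 1/(n·m), which does grow without limit.

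**3. Adjusted fits at k v 0, 120 per arm.** About 400 to 1,000 simulated data sets per cell, in R 4.3.3 and Python. Main assumptions: age about N(65, 11) limited to 18–80; 65% male; NIHSS negative binomial with mean 6, capped at 25; onset time uniform over 60–270 min; covariates either unrelated to the event or related (log RR 0.04 per year and 0.12 per NIHSS point).

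| Events | 1/√k | Median HC0 SE | P<0.05, HC0 | P<0.05, HC3 (R) | χ² P | Fisher P |
|---|---|---|---|---|---|---|
| 1 v 0 | 1.00 | 1.0 | about 98% | 53–67% | 0.32 | 1.00 |
| 2 v 0 | 0.71 | 0.7 | 99.6–100% | 90–97% | 0.16 | 0.50 |
| 3 v 0 | 0.58 | 0.6 | 100% | 98–99.8% | 0.08 | 0.25 |

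HC1 agrees with HC0 to within 0.1 points in R. The χ² column follows from χ² = 2nk/(2n − k): 240/239 = 1.00, 480/238 = 2.02 and 720/237 = 3.04. Across implementations the 1 v 0 figure with HC0 or HC1 ran from 95.8% to 99.8%. The fitted log RR at 1 v 0 is about 19 with a standard error of about 1.0, so z is about 19; the exact value depends on the software's stopping rule.

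**4. The fault is specific to the empty arm and the robust variance.** At 2 or 3 v 1 the same model rejects in about 1% of fits or fewer. With the model-based standard error at default tolerance, the k v 0 fits reject in 0.1% or fewer.

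**5. How often one arm is empty.** With equal true rate p and q = (1 − p)^120, the chance that exactly one arm is empty is 2q(1 − q).

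| p (assumed) | q | 2q(1 − q) |
|---|---|---|
| 1% | 0.299 | 42.0% |
| 2% | 0.0885 | 16.1% |
| 3% | 0.0259 | 5.0% |
| 4% | 0.0075 | 1.5% |

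With 114 per arm the values are 43.4, 18.0, 6.0 and 1.9%. Because nearly every such trial rejects, null rejection of the adjusted model is about 42% at a 1% rate and about 17% at 2%. At 3% it is 5.5–7.4% and at 4% it is 4.2–4.6%.

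**The case against.** **Exploratory status.** Section 2.3 files these outcomes under secondary safety, and section 11.2 says that "findings for secondary outcome analyses should be interpreted as exploratory". That caveat can be read to cover them, and it limits the consequences. But it addresses multiplicity; it does not make an invalid P value valid.

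**An analyst would notice.** A log RR near 19 is plainly absurd, and a χ² P of 0.32 would stand beside it. That is fair, but the plan does not say what to do then. Convergence warnings are not a dependable guard: about 34–51% of R fits at 1 v 0 failed to converge, but only 3–10% at 2 v 0 and about 1% or fewer at 3 v 0.

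**Variance type and software.** A reader might infer that the planned model rejects whatever the count and whatever the software. The documents do not support that. They name no sandwich type, and HC3 lowers the 1 v 0 figure to 53–67%. SPSS and R 4.1.0 were not tested.

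**Reach.** A reader might also infer that symptomatic ICH is bound to be affected, because section 3.2.2 excludes "Haemorrhage during IVT, including ICH, severe digestive haemorrhage and severe respiratory haemorrhage". That exclusion removes only bleeds up to the end of thrombolysis, while the outcome runs to 7 days, and it applies to any ICH alike. Likewise, the 100 − 49.3 = 50.7% of controls expected at mRS 3–6 does not give a death rate. Whether an arm will be empty cannot be settled from the documents.

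**Conclusion.** The gap is real and minor. For any binary outcome with an empty arm, the stated adjusted model gives a P value that should not be used, and it contradicts the plan's own χ² test with no rule on which governs. With the usual HC0/HC1 variance this affects about 98% of fits at 1 v 0 and essentially all from 2 v 0.

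The practical reach rests on assumed event rates: substantial at 1–2%, slight at 3%, and gone by about 4%. The fitted percentages rest on assumed covariate distributions, but the mechanism in step 2 does not. The primary outcome is unaffected, since its expected proportions are far from zero. Nothing here supports the inference that the trial's safety assessment as a whole is unsound; what is missing is a fallback for one sparse-data case.

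**What to change.** Add to section 11.2 and the synopsis, before unblinding:

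> For any binary outcome with zero events in either arm, the modified Poisson RR, CI and P value are not reported. Counts and the risk difference with a Newcombe 95% CI are given as description, and Fisher's exact test replaces the χ² test and is the governing test result. A non-significant P value is not read as evidence of safety.

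Name one interval in advance: at 4 v 0 Newcombe gives −0.4 to 8.3 points and Miettinen–Nurminen 0.2 to 8.3, so a free choice would decide whether zero is excluded. The last sentence is needed because even 0 v 0 leaves a Newcombe interval of −3.1 to 3.1 points.

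With this rule (HC0 otherwise), simulated null rejection at rates of 1, 2, 3 and 4% is 2.7, 3.3, 3.3 and 3.6% with related covariates, and 0.5, 1.2, 1.8 and 2.8% with unrelated ones.

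The cost is three sentences and no new data. Fisher's test is conservative: 6 v 0 is needed for P<0.05 (P=0.029). At 5 v 0 P is 0.060 although the Newcombe interval, 0.3 to 9.4 points, excludes zero, which is why the wording says which result governs. Outcomes with an empty arm also get no adjusted RR. A prespecified penalised model would be an acceptable alternative if an adjusted estimate is wanted.

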6.3 Clinical observation

National Institutes of Health Stroke Scale (NIHSS) is commonly used to evaluate neurological deficits in patients with AIS and includes 15 items in 11 fields of different neurological statuses. The NIHSS is scored at admission, at the end of IVT, 24-h and 7-day after randomization during hospitalization.

END indicates an increase of ≥ 2 or ≥ 4 in the NIHSS score within 24 h after IVT, and the deterioration is not caused by ICH, which is confirmed by cranial CT.

Modified Rankin Scale (mRS) reflects disability at follow-up time, which consists of 7 disability levels, ranging from 0 (no symptoms) to 5 (severe disability), and 6 (death). We intend to assess the mRS on days 7, 30, and 90 after randomization.

Barthel index (BI) is a standardized tool used to evaluate a person's ability to perform basic activities of daily living independently at follow-up time, and consists of 10 items, ranging from 0 (total dependence) to 100 (complete independence). We intend to assess the BI on days 30 and 90 after randomization.

The ejection fraction is assessed by ultrasonic cardiogram within 72 hours after randomization.

Blood pressure, including systolic blood pressure (SBP) and diastolic blood pressure (DBP), is monitored from IVT initiation every 5 min for 2 h and then continuously assessed every 30 min for 6 h and every hour for 16 h. The 24-hour blood pressures are recorded (before IVT, after IVT, 10 hours, 12 hours and 24 hours after randomization).

7. Outcomes

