7.1.2 Secondary outcomes

(1) Proportion of patients with END (Δ NIHSS ≥ 2 and Δ NIHSS ≥ 4) at 24 hours after randomization.

Δ NIHSS indicates 24-hour NIHSS score minus post-IVT NIHSS score.

(2) Proportion of patients with cerebrovascular events within 1 day, 7 days and 90 days after randomization. Cerebrovascular events included progressive stroke (NIHSS deterioration ≥ 2 scores),

transient ischemic attack or new ischemic lesions confirmed by imaging.

(3) NIHSS scores at 7 days.

(4) Proportion of patients with mRS 0-2 at 30 days.

(5) mRS distribution at 30 days and 90 days.

(6) BI scores at 30 days and 90 days.

(7) Proportion of the patients with BI 60-100 at 30 days and 90 days.

(8) Peripheral blood inflammatory indices, including neutrophil-to-lymphocyte ratio (NLR), platelet-to-lymphocyte (PLR), lymphocyte-to-monocyte (LMR) and (platelet \times neutrophil)/lymphocyte (SII) at 24-48 hours after randomization.

(9) Laboratory examinations (S100- β , BDNF, and MPO) at 24-48 hours after randomization.

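### Section 11.2 gives no rule for deaths in the 7-day NIHSS and the 30- and 90-day Barthel analyses, so the models as written would compare survivors only

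*Combined protocol and SAP*

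**What the plan says.** Section 7.1.2 lists "NIHSS scores at 7 days" and "BI scores at 30 days and 90 days" among the secondary outcomes, and also "Proportion of the patients with BI 60-100 at 30 days and 90 days". For the scores, 11.2 names generalized linear models (GLMs), which "are conducted for analyse continuous end points, including NIHSS scores, Barthel scale, blood pressure" and two further measures, at every follow-up visit. Dichotomous end points go to a modified Poisson model.

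Section 6.3 and the appendices define the scales. The mRS has a level for death, "ranging from 0 (no symptoms) to 5 (severe disability), and 6 (death"). The BI does not, "ranging from 0 (total dependence) to 100 (complete independence"), and the NIHSS items in Appendix 1 score neurological findings only.

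Section 11.2 has two rules for missing data. One is a sensitivity analysis of the primary outcome, "imputation of missing primary outcome data under the scenarios of worst possible outcome, and best possible outcome". The other is mean or mode replacement, for baseline covariates only. Neither reaches the NIHSS or the BI. Death within 90 days is a separate safety outcome (7.2), and 11.2 labels the secondary findings exploratory.

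**The concern.** A patient who has died has no BI or NIHSS score. If nothing assigns one, a GLM fitted to the score leaves that patient out. Death occurs after randomization and may depend on treatment, so the patients left in the model are no longer the randomized groups. Deaths tend to come from patients who would otherwise have scored badly. An arm with extra deaths therefore loses its worst scores and its average improves. The reverse also holds: an arm that keeps severely affected patients alive can look worse.

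Unequal mortality cannot be ruled out from the plan itself. Section 10.1 lists acute heart failure, pulmonary edema and severe cerebral edema among the events that may be associated with the interventions, and 3.2.1 admits patients up to age 80 with NIHSS up to 25. At stake is whether the BI and NIHSS results could seem to support a benefit while mortality points the other way.

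**Working it through.** **What the plan gives.** There is no stated figure for the NIHSS or BI analyses, and no expected mortality or score distribution. The only figure borrowed is the arm size of 120 from 11.1. It reproduces with an unpooled two-proportion calculation: (1.960 + 0.842)² × (0.673 × 0.327 + 0.493 × 0.507) / 0.18² gives 114, and 114 / 0.95 = 120. The point does not dispute it.

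**Does any rule cover deaths?** The full analysis set in 11.2 needs randomization and at least one efficacy evaluation. A patient with a 24-hour NIHSS who dies on day 20 is in that set but has no 30- or 90-day BI. The set decides who belongs; it does not say what score a dead patient receives. The intention-to-treat definition in 11.3.1 has the same limit.

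**BI illustration (assumed inputs).** Both arms have 120 patients with the same prognosis, and 6 die in each arm regardless. In one arm, *e* further patients die who in the other arm would have survived with BI = *L*. The remaining 114 − *e* survivors average 80.

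- Survivors only: the arm with more deaths averages 80; the other averages [80(114 − *e*) + *Le*] / 114. Difference = *e*(80 − *L*) / 114.
- Death scored 0, all 120 in the denominator: difference = −*eL* / 120.

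For *e* = 6 and *L* = 10: survivors only, 80 − 8700/114 = 80 − 76.32 = +3.68; death as 0, 8640/120 − 8700/120 = 72.0 − 72.5 = −0.50.

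| Extra deaths | Deaths, two arms | Would-be BI | Survivors only | Death as 0 |
|---|---|---|---|---|
| 3 | 9 vs 6 | 10 | +1.84 | −0.25 |
| 3 | 9 vs 6 | 30 | +1.32 | −0.75 |
| 6 | 12 vs 6 | 10 | +3.68 | −0.50 |
| 6 | 12 vs 6 | 30 | +2.63 | −1.50 |
| 12 | 18 vs 6 | 10 | +7.37 | −1.00 |
| 12 | 18 vs 6 | 30 | +5.26 | −3.00 |

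Positive values favour the arm with more deaths. The sign differs between the two columns in every row.

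**NIHSS at day 7 (assumed inputs).** Two patients die in each arm regardless; 2, 4 or 6 more die in one arm who would have scored 20; the other survivors average 5. Survivors only: −*e*(20 − 5)/118 = −0.25, −0.51, −0.76, which favours the arm with more deaths because lower is better. With death scored 42, the sum of the Appendix 1 item maxima: +*e*(42 − 20)/120 = +0.37, +0.73, +1.10, against it.

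**BI 60-100.** Use the BI inputs, with 75% of the other survivors reaching 60 and none of the extra patients who die. A survivors-only denominator gives RR = 114/(114 − *e*) = 1.03, 1.06, 1.12 for *e* = 3, 6, 12. With all 120 in each denominator the RR is 1.00. This matters only if the denominator is patients with a BI score.

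**The case against.** The strongest reply is that death is already captured where it counts. The primary outcome and the ordinal mRS analysis score it as 6, the mRS distribution is analysed at 30 and 90 days beside the BI, and mortality is reported in its own right. An arm with more deaths would show it there. The affected outcomes are exploratory, and eligibility (no massive infarction, heart failure or terminal illness) should limit deaths, particularly by day 7. All of this stands, and it limits the consequences. It does not remove the selection: the exploratory label in 11.2 addresses multiplicity, not bias.

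The illustration also rests on chosen inputs. If the BI standard deviation is 25 to 35 (an assumption), the standard error of the difference with about 110 per arm is SD × √(2/110), or 3.4 to 4.7. With 6 extra deaths the artefact is then about 0.6 (2.6/4.7) to 1.1 (3.7/3.4) standard errors. The negative differences with death scored 0 are small on a 100-point scale. The contrast shows that the handling of deaths can decide the sign; it does not forecast a result.

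Three stronger readings are tempting, and the documents do not support them.

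- *The plan excludes deaths.* It does not say so; it is silent. A survivors-only comparison is what results when a GLM is fitted to a score that a dead patient cannot have.
- *The BI 60-100 proportions are equally affected.* Section 7.1.2 speaks of a proportion of the patients, and the analysis set in 11.2 does not depend on having a BI score. The more natural denominator is the full analysis set, with deaths as not achieved. This needs a clarifying sentence only.
- *The saline arm will be flattered.* No document gives mortality by arm. The direction depends on which arm has more deaths and on who dies.

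**Conclusion.** The concern holds for three exploratory secondary outcomes: BI at 30 days, BI at 90 days and, with less force, NIHSS at 7 days. For these the stated method would compare survivors only, and it could favour the arm with more deaths. The range of +1.3 to +7.4 BI points for survivors only, against −0.3 to −3.0 with death as 0, rests on 3 to 12 extra deaths per 120, would-be BI of 10 to 30 and an average of 80 in the other survivors. None of these three inputs comes from the documents. If mortality is equal and affects similar patients in both arms, there is no distortion. The primary result, the ordinal mRS analysis and the sample size are unaffected. The change should be made, but the main conclusion of the trial does not depend on it.

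**What to change.** In 11.2:

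1. For 7-day NIHSS and for BI at 30 and 90 days, give deaths the worst rank, below the worst living score, and compare the arms with a rank-based or ordinal model. A worst rank is cleaner than BI 0, because 0 is also the score of a living, totally dependent patient.
2. State that deaths count as not achieving BI 60-100, with the full analysis set as the denominator.
3. Keep the survivors-only GLM as a supportive analysis, labelled as such, with the number of deaths shown by arm.

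The rule should be written down before outcomes are seen by arm. The cost is a few sentences and a few lines of code; no new data are needed. The downside is that the score contrast then mixes death with function, which the supportive analysis separates.

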Statistical analysis	The primary outcome is performed in the intention-to-treat populations as well as per-protocol populations. Sensitivity analyses are performed as well in order to find out the influence factors. The χ^2 test is used in the unadjusted analysis. Modified Poisson regression model with robust error estimation is used in analysis of the primary outcome and other dichotomous end points, with adjustment for prespecified covariates. The relative risk with their 95% confidence interval is calculated in both unadjusted and adjusted analysis. Generalized linear models are conducted for analyse continuous end points. The full range score on mRS is analyzed by an ordinal logistic-regression model, and odds ratios with 95% confidence interval are calculated. No interim analyses are performed in this study. A 2-sided P value <0.05 is considered statistical significance. Because multiple comparisons potentially cause type I error, findings for secondary outcome analyses should be interpreted as exploratory. SPSS software (version 26, IBM) and R software (version 4.1.0) are used for the statistical analyses.
Sites Number	3 centers
Collaborators	Affiliated Hospital of Jiujiang University Cangzhou Hospital of Integrated Traditional Chinese and Western Medicine
Duration	Enrollment about 1 year

Abbreviation

END, early neurological deterioration

NIHSS, National Institutes of Health Stroke Scale

mRS, Modified Ranking Scale

BI, Barthel Index

ICH, intracranial hemorrhage

IVT, intravenous thrombolysis

AIS, acute ischemic stroke

CBF, cerebral blood flow

NS, normal saline

ESO, European Stroke Organisation

CT, computed tomography

MRI, magnetic resonance imaging

BNP, brain natriuretic peptide

MBP, myelin basic protein

GFAP, glial fibrillary acidic protein

MRA, magnetic resonance angiography

CTA, CT angiography

SBP, systolic blood pressure

DBP, diastolic blood pressure

NLR, neutrophil-to-lymphocyte ratio

PLR, platelet-to-lymphocyte

LMR, lymphocyte-to-monocyte

AEs, adverse events

SAEs, serious adverse events

RR, relative risk

GLMs, Generalized linear models

OR, odds ratio

ITT, Intention-To-Treat

PP, Per protocol

CRF, Case Report Forms

1. Background

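### Covariates are named only for the dichotomous end points; the ordinal mRS model (like the GLMs and the Cox model) has none, so the shift analysis forgoes available precision

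*Combined protocol and SAP*

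**What the plan says.** Section 11.2 (Statistical analysis) names a covariate set once, inside the sentence on modified Poisson regression for the primary outcome and the other dichotomous end points: "age, sex, post-IVT NIHSS scores and onset-to-needle time". It promises unadjusted and adjusted results only for the relative risk.

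The other models are listed without covariates:

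- Ordinal mRS: "The full range score on mRS is analyzed by an ordinal logistic-regression model, and odds ratio (OR) with 95%CI are calculated".
- Continuous end points (NIHSS, Barthel, blood pressure, infarct volume, ejection fraction): generalized linear models, no covariates listed.
- Follow-up cerebrovascular events: Cox regression, no covariates listed.

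The synopsis repeats the pattern. It attaches prespecified covariates to the modified Poisson model without naming them, then says: "The full range score on mRS is analyzed by an ordinal logistic-regression model, and odds ratios with 95% confidence interval are calculated". It does not mention the Cox model.

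The rule in Section 11.2 for missing baseline values refers to covariate-adjusted analyses in general and does not say which models those are. Section 7.1.2 lists the mRS distribution at 30 and 90 days as secondary outcome (5). Section 11.2 treats secondary findings as exploratory, and no power is stated for them.

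**The concern.** The same 90-day mRS scores are analysed under two rules. The 0-2 split is adjusted; the full seven-level scale has no stated adjustment. The plan itself regards age and post-IVT NIHSS as worth adjusting for, and both can be expected to predict mRS. In proportional-odds and Cox models, leaving out a strong predictor moves the estimated OR or HR towards 1 and lowers power, even when the arms are perfectly balanced.

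Two things are at stake. One is precision in the analysis that uses the whole mRS scale. The other is prespecification: in an open-label trial, covariates left unstated for three model families allow a choice between adjusted and unadjusted estimates after the data are seen.

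**Working it through.** **Inputs from the documents.** Section 11.1 gives the effect ("67.3% in the NS group and 49.3% in the control group"), the power ("Based on 0.8 power to detect a significant difference"), 5% nonadherence or dropout, and the size ("we intend to enroll 120 patients per group"). Section 11.2 gives the test level ("A 2-sided P value <0.05 is considered statistical significance").

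**1. The plan's own sample size.** Two proportions, unpooled variance:

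n = (1.96 + 0.8416)² × (0.673×0.327 + 0.493×0.507) / 0.18² = 7.849 × (0.2201 + 0.2500) / 0.0324 = 113.9, so 114 per group.

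114 / 0.95 = 120 per group. The stated figure reproduces, with 2 × 114 = 228 evaluable patients.

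**2. Implied odds ratio.** (0.673/0.327) / (0.493/0.507) = 2.058 / 0.972 = 2.12.

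**3. Unadjusted power of the shift test at that effect.** The documents give no mRS category distribution. Assumed control distribution for mRS 0 to 6: 13, 20, 16.3, 13, 15, 7.7 and 15%, which puts 49.3% at 0-2. Whitehead's formula:

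- V = (N/12) × (1 − Σ p̄³), where p̄ is the mean of the two arms' category proportions. With N = 228 and Σ p̄³ = 0.0289, V = 19 × 0.9711 = 18.45.
- Power = Φ(ln 2.117 × √18.45 − 1.96) = Φ(3.22 − 1.96) = Φ(1.26) = 0.896.
- The same steps with OR 1.6 (an assumed smaller effect) give 0.524.

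**4. Gain from adjustment, by simulation.** Seven-level proportional-odds data, 228 patients, four independent normal covariates with the stand-in for post-IVT NIHSS dominant, Wald test at two-sided 0.05, 700 to 1,500 runs per cell. Covariate strength is expressed as the share of latent mRS variance explained (R²). The documents give no value for it, so it is varied. Each cell shows unadjusted to adjusted power in %, with the gain in points.

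| Latent R² | OR 2.12 marginal | OR 2.12 conditional | OR 1.6 marginal |
|---|---|---|---|
| 0.07 | 89.3 to 91.0 (1.7) | 87.7 to 90.4 (2.7) | 54.6 to 57.3 (2.7) |
| 0.15 | 89.1 to 94.6 (5.5) | 83.5 to 90.1 (6.5) | 54.3 to 61.1 (6.8) |
| 0.23 | 91.3 to 96.4 (5.1) | 77.8 to 88.8 (11.0) | 54.1 to 64.9 (10.8) |
| 0.32 | 89.7 to 97.9 (8.2) | 71.9 to 86.6 (14.7) | 52.8 to 71.9 (19.1) |
| 0.41 | 91.6 to 99.5 (7.9) | 67.2 to 88.6 (21.4) | 57.5 to 79.1 (21.5) |
| 0.55 | 89.4 to 99.9 (10.4) | 55.1 to 87.7 (32.6) | 55.7 to 87.4 (31.7) |

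Gains were taken before rounding. Monte Carlo error is about 1 to 2.5 points per cell; separate runs of two OR 1.6 cells gave 15.6 points at R² 0.23 and 24.7 at 0.41.

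**5. Reading the table.** In the marginal columns the visible arm difference is held fixed. In the conditional column the covariate-specific OR is held fixed, so the visible arm difference shrinks as R² rises; that shrinkage produces the falling unadjusted power. Section 11.1 plans a difference in observed proportions, so the first column is the natural match to the plan.

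**6. Cox model.** The documents give no event rate and no hazard ratio, so there is nothing to compute.

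**The case against.** The strongest reply is that little is lost. At the planned effect the unadjusted shift test already has about 90% power, above the 80% set for the primary. The analysis is secondary and exploratory with no power target, and the primary already has prespecified adjustment. All of this stands, and it limits the weight of the point.

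A reader might go further than the documents allow in five ways:

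- **That the shift analysis is underpowered, or loses 10 to 25 points of power.** At the planned marginal effect the gain is about 2 to 10 points. Gains of 10 to 25 need a conditional reading of the OR or a smaller effect, with covariates explaining roughly 23 to 41% of latent variance.
- **That the sponsor decided against adjustment.** Section 11.2 never says the ordinal, GLM or Cox analyses are unadjusted; it lists no covariates. Followed literally the ordinal model is unadjusted, but the intention is unknown.
- **That the unadjusted OR is biased.** Under randomisation it is a valid marginal estimate. The adjusted OR is a conditional one, and the two differ because odds ratios are non-collapsible.
- **That the ordinal result has no binary counterpart.** The RR is reported unadjusted as well as adjusted, and an OR and an RR sit on different scales in any case.
- **That the Cox model loses a known amount of power.** Nothing in the documents supports a figure, and with few events four covariates could be too many.

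None of this answers the narrower point: the covariates exist, are named, and are not attached to these models.

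**Conclusion.** The point holds as a gap in specification with a nearly free improvement. Adjusting the ordinal model raised power in every scenario simulated, from about 2 to about 33 points. The lower part of that range (about 2 to 10) applies if 67.3% versus 49.3% is the marginal effect; the upper part (roughly 25 to 33) needs a conditional OR or a smaller true effect together with strong covariates. These figures rest on an assumed mRS distribution, proportional odds, and assumed covariate strength, so none should be read as the trial's actual loss. The GLMs share the gap but were not simulated. The primary analysis is unaffected.

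**What to change.** In Section 11.2 and the synopsis:

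- State that the ordinal logistic model for the 30- and 90-day mRS is adjusted for age, sex, post-IVT NIHSS and onset-to-needle time, with age and NIHSS continuous. Make the adjusted common OR the main reported estimate and show the unadjusted OR beside it.
- Apply the same four covariates to the GLMs.
- Apply them to the Cox model if the number of events supports four covariates, and say in advance how that will be judged.
- Say which models the rule for missing baseline values covers.

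The cost is wording only, since the covariates are already collected and used for the primary. The small downside is that the adjusted OR is conditional and will differ numerically from the unadjusted marginal OR; a sentence in the plan should say so.
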